3.4. Dosing Considerations

3.4.1.1. Nanatinostat and Valganciclovir

In Phase 1b, the nanatinostat starting dose of 20 mg orally once daily on Days 1 to 4 per week in combination with the standard valganciclovir dose 900 mg orally once daily is based on the preliminary results (as of 27 Oct 2021; n=55) from the Phase 1b/2 VT3996-201 study in patients with EBV⁺ relapsed or refractory lymphomas. This patient population was heavily pretreated (77% received ≥2 prior therapies; median number of prior therapies was 2, range 1-11), the majority (75%) of whom had disease that was refractory to their last therapy at study entry. Most patients received repeat cycles of various cytotoxic regimens, including alkylating agents, anthracyclines, vinca alkaloids, and various biologic agents; the majority of these agents are associated with cytopenias. Nanatinostat in combination with valganciclovir has been generally well tolerated in this patient population (Section 1.5.1.1).

Based on the safety data from previous cohorts, dosing with nanatinostat and valganciclovir will continue in single or split daily doses of nanatinostat with single daily or split daily doses of

valganciclovir beginning with intermittent nanatinostat dosing on Days 1 to 4 and escalating to twice daily dosing of nanatinostat and valganciclovir on Days 1 to 7 per week until the RP2D is determined.

3.4.1.2. Nanatinostat, Valganciclovir, and Pembrolizumab

According to the prescribing information, the recommended dose and schedule of pembrolizumab is 200 mg IV every 3 weeks (Keytruda [pembrolizumab] Prescribing Information, 2023). This dose and schedule of pembrolizumab has been safely combined with a number of cytotoxic chemotherapy regimens and biologic agents. For valganciclovir, although most toxicities reported are mild to moderate in nature, the prescribing information carries a warning regarding the development of cytopenia and renal toxicity (Valcyte [valganciclovir] Prescribing Information, 2021).

To date, the most commonly reported toxicities with nanatinostat and valganciclovir at the RP2D (n=42) in the VT3996-201 study include nausea and cytopenias (additional details are provided in the latest version of the nanatinostat IB). The potential for overlapping toxicities with nanatinostat, valganciclovir, and pembrolizumab may be highest for renal function (already mitigated by the frequent monitoring of renal function according to the prescribing information for valganciclovir) and gastrointestinal events such as nausea and vomiting.

Following dose escalation, two additional cohorts with up to 20 patients each will be randomized to receive nanatinostat and valganciclovir in the dose optimization cohort period at the RP2D and <RP2D to be selected in consultation with the SMC. After a review of the data from the first two cycles of the dose optimization cohort period, enrollment into Phase 2 dose expansion will begin, supported by an early safety analysis of the first 6 patients randomized to receive nanatinostat and valganciclovir with pembrolizumab as described in Section 5.5.3.3.

4. SELECTION OF STUDY POPULATION

Patients must have a histologically confirmed diagnosis of EBV⁺ recurrent or metastatic NPC or other solid tumor type and received previous systemic therapy for their cancer; have measurable disease determined by magnetic resonance imaging (MRI) or computed tomography (CT) with contrast at screening; and have adequate bone marrow, liver, and renal function.

4.1. Patient Population

4.2. Inclusion Criteria

To be eligible for study participation, patients must meet all of the following inclusion criteria:

- 1. Adult patients age \geq 18 years.
- 2. Willing and able to give informed consent.
- 3. Histologically or cytologically documented EBV⁺ tumor cells by EBER-ISH or LMP-1 (according to local guidelines) per an archival tumor sample taken within 2 years prior to screening, otherwise a de novo biopsy may be required. FFPE tissue block(s) or at least 10 unstained slides are requested. It is encouraged (but not required) that patients with a

- site of disease accessible to biopsy and who are candidates for tumor biopsy according to local practice guidelines undergo a new tumor biopsy at baseline and during treatment.
- 4. Patients with RM-NPC (excluding patients in the Phase 1b exploratory proof-of-concept cohort) for whom no potentially curative options are available, who have received at least 1 prior line of platinum-based chemotherapy and no more than 3 prior lines of therapy for RM-NPC.

Note: The following clinical scenarios are not considered to be separate lines of therapy:

- a. Maintenance therapy: drug therapy (including chemotherapy, targeted therapy, or immunotherapy including vaccines, cellular therapy, and checkpoint inhibitors) that is started with maintenance intent in patients who have recently completed one line of chemotherapy without experiencing disease progression.
- b. Drug rechallenge: patients who have been "rechallenged" with the same drug therapy(s) previously used to treat recurrent or metastatic NPC.
- 5. Patients who developed recurrent or metastatic disease within six months following radical concurrent chemoradiotherapy in combination with neoadjuvant and/or adjuvant therapy for non-metastatic NPC are eligible as long as no potentially curative options are available.
- 6. **For Phase 1b exploratory proof-of-concept cohort only:** Patients with advanced/metastatic EBV⁺ non-NPC solid tumors (gastric cancer, LELC, leiomyosarcoma) that have progressed despite standard therapy for which no curative therapies exist.
- 7. Radiologically measurable disease per RECIST v1.1.
- 8. All acute toxic effects of any prior anti-neoplastic therapy resolved to at least Grade 1 before initiation of study treatment (excluding alopecia, Grade 2 sensory neuropathy, hypothyroidism [stable on thyroid hormone supplementation], chronic/stable xerostomia, hearing loss, lymphedema, and taste changes [all Grade 2]).
- 9. Eastern Cooperative Oncology Group (ECOG) performance status 0 or 1.
- 10. Life expectancy ≥ 3 months.
- 11. Adequate laboratory parameters (in the absence of transfusion or growth factor support with 3 weeks of Screening) including:
 - a. Absolute neutrophil count $\geq 1500/\text{mm}^3$.
 - b. Platelets count $\geq 100,000/\text{mm}^3$.
 - c. Hemoglobin ≥9.0 g/dL.
 - d. Aspartate aminotransferase (AST)/serum glutamine oxaloacetic transaminase (SGOT), alanine aminotransferase (ALT)/serum glutamic- pyruvic transaminase (SGPT) ≤2.5 × upper limit of normal (ULN) (≤5 × ULN if known liver involvement by tumor).
 - e. Total bilirubin \leq 2.0 × ULN unless considered due to Gilbert's syndrome in which case, \leq 3.5 × ULN.
 - f. Estimated glomerular filtration rate ≥60 mL/min by Cockcroft-Gault equation (see Section 5.6.2 for formula to calculate creatinine clearance).

- g. Prothrombin time (PT) or international normalized ratio \leq 1.5 × ULN.
- h. Serum potassium and magnesium should be within normal limits for institution or treatment to correct out of range values should be instituted.
- 12. For HIV positive patients:
 - a. CD4 count \geq 350 cells/ μ L.
 - b. On an established antiretroviral therapy (ART) for ≥ 4 weeks.
 - c. An undetectable HIV viral load.
 - d. No prior AIDS-defining opportunistic infections within the past 12 months.
- 13. Willingness to comply with study requirements.
- 14. Women of childbearing potential (ie, reached menarche, and not post-menopausal [no menses for 12 months without an alternative medical cause] or surgically sterile) must have the following:
 - a. Understand that the study medication is expected to have teratogenic risk.
 - b. Have a negative serum beta human-chorionic gonadotropin pregnancy test at screening.
 - c. Commit to continued abstinence from heterosexual intercourse (excluding periodic abstinence or the withdrawal method) or commit to the use of 2 forms of birth control with at least one highly effective method of birth control with a Pearl-Index <1%, and one effective barrier method such as a male condom, female condom, cervical cap, diaphragm, or contraceptive sponge with spermicide, without interruption, throughout the study dosing period and for 6 months after the last dose of study treatment. Apart from abstinence, highly effective methods of birth control include the following:
 - i. Combined (estrogen- and progestogen-containing) hormonal contraception associated with inhibition of ovulation (ie, intravaginal, transdermal). Please note: Although the potential for drug interactions and risk of venous thromboembolism is low (see Section 5.7.2.3), the use of an alternative method of contraception is recommended.
 - ii. Progestogen-only hormonal contraception associated with inhibition of ovulation (oral, injectable, implantable).
 - iii. Intrauterine device
 - iv. Intrauterine hormone-releasing system
 - v. Bilateral tubal occlusion.
 - vi. Vasectomized partner.
- 15. Male patients must agree to use condoms during intercourse throughout the study dosing period and for 90 days after the last dose of study treatment.

4.3. Exclusion Criteria

Patients meeting any of the following criteria will be excluded from the study:

1. Anti-tumor treatment with cytotoxic drugs, biologic therapy (eg, monoclonal antibody), immunotherapy, or other investigational drugs within 4 weeks or >5 half-lives, whichever is shorter.

- 2. Corticosteroids within 7 days prior to dosing (unless ≤10 mg/day of prednisone or equivalent).
- 3. For NPC:
 - a. Active parenchymal or leptomeningeal metastases.
 - b. Base of skull disease that poses a risk of significant bleeding (eg, proximity to carotid artery) as judged by the Investigator.
 - c. Invasive disease for which there is a potential risk of significant bleeding as judged by the Investigator.
- 4. For non-NPC cancers: Active central nervous system (CNS) disease/metastases.
- 5. Nasopharyngeal cancer patients who have received prior therapy with an anti-PD-1 agent are not excluded, except for those who experienced prior Grade 3 or higher immunerelated toxicity that resulted in permanent drug discontinuation (patients with prior temporary drug interruptions due to endocrinopathies etc. are eligible).
- 6. Less than 14 days from prior locoregional site radiotherapy. Palliative radiotherapy outside the head and neck is allowed as long as the lesions are not target lesions.
- 7. Tumor mutational burden -high advanced malignancies and/or microsatellite instability-high malignancies who would otherwise be eligible for pembrolizumab (unless patients have progressed on pembrolizumab) in accordance with local standards, (ie, only if such biomarkers are performed as standard of care in the participating center).
- 8. Major surgery, open biopsy, or significant traumatic injury within 28 days prior to starting study treatment. In case of recent major surgery, the patient must have recovered adequately from the procedure and/or any complications prior to starting study treatment.
- 9. Is currently participating in or has participated in an interventional study of an investigational agent or has used an investigational device within 4 weeks prior to the first dose of study treatment.

Note: Individuals who have entered the follow-up phase of an investigational study may participate as long as it has been 4 weeks since the last dose of the previous investigational agent.

- 10. Diagnosis of any other malignancy within 3 years prior to enrollment, except for the following if adequately treated:
 - local basal cell or squamous cell carcinoma of the skin, or related localized non-melanoma skin cancer.
 - carcinoma in situ of the breast or of the cervix.
 - superficial bladder cancer.
 - low grade (Gleason 6 or below) prostate cancer undergoing surveillance with no plans for treatment intervention or previously fully resected.
- 11. Gastrointestinal abnormalities including the following:
 - Inability to take oral medication.
 - Malabsorption syndrome or any other gastrointestinal condition (nausea, diarrhea,

vomiting) that may impact the absorption of nanatinostat and valganciclovir.

- Prior surgical procedures affecting absorption including total gastric resection.
- Active gastrointestinal bleeding (hematemesis, hematochezia, or melena) in the past 3 months without documentation of resolution by endoscopy/colonoscopy.
- 12. Positive surface antigen unless quantitative DNA polymerase chain reaction (PCR) is undetectable, and patient is stable on antiviral prophylaxis against hepatitis B virus (HBV) reactivation. Patients who are hepatitis B core antibody positive must have undetectable quantitative DNA PCR and be monitored according to the local standard-of-care/institutional guidelines.
- 13. Positive hepatitis C virus on RNA PCR.
- 14. Known SARS-CoV-2 positivity at time of screening (patients can be re-screened once negative by PCR).
- 15. History of allergic reactions attributed to compounds of similar chemical or biologic composition to valganciclovir or nanatinostat.
- 16. Active infection requiring systemic therapy.
- 17. Prolongation of corrected QT interval using Fridericia's formula (QTcF) to >480 msec, requires the coadministration of drugs known to prolong QT (Class Ia [disopyramide, quinidine, procainamide] and Class III [sotalol, dofetilide, ibutilide] antiarrhythmic agents) (Drew 2010), and/or has a history of Torsades de Pointes (TdP).
- 18. Receiving potentially nephrotoxic drugs (eg, cyclosporin).
- 19. Receiving concomitant drugs that are inhibitors of P-glycoprotein (P-gp) and breast cancer resistance protein (BCRP), unless they can be held for 2 weeks or 5 half-lives, whichever is longer, prior to administration of nanatinostat. See Appendix 1, Table 2 for a list of drugs.
- 20. Receiving tenofovir (unless can be switched to an alternative ART).
- 21. Psychiatric illness/social situations/substance abuse disorder that would interfere with compliance with study requirements.
- 22. Active autoimmune disease that has required systemic therapy with modifying agents, corticosteroids, or immunosuppressive agents.
- 23. Prior or ongoing clinically significant illness, medical condition, physical finding, electrocardiogram (ECG) finding, or laboratory abnormality that, in the Investigator's opinion, could affect the safety of the patient, impair the assessment of study results, interfere with the patient's participation for the full duration of the study, or is not in the best interest of the patient to participate.
- 24. Females who are pregnant or breastfeeding or expecting to conceive children within the projected duration of the study, starting with the screening visit through 6 months after the last dose of study treatment.

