- 5. Nasopharyngeal cancer patients who have received prior therapy with an anti-PD-1 agent are not excluded, except for those who experienced prior Grade 3 or higher immune-related toxicity that resulted in permanent drug discontinuation (patients with prior temporary drug interruptions due to endocrinopathies etc. are eligible).
- 6. Less than 14 days from prior locoregional radiotherapy. Palliative radiotherapy outside the head and neck is allowed as long as the lesions are not target lesions.
- 7. Tumor mutational burden (TMB) -high advanced malignancies and/or microsatellite instability (MSI) -high malignancies who would otherwise be eligible for pembrolizumab (unless patients have progressed on pembrolizumab) in accordance with local standards (ie, only if such biomarkers are performed as standard of care in the participating center).
- 8. Major surgery, open biopsy, or significant traumatic injury within 28 days prior to starting study treatment. In case of recent major surgery, the patient must have recovered adequately from the procedure and/or any complications prior to starting study treatment.
- 9. Is currently participating in or has participated in an interventional study of an investigational agent or has used an investigational device within 4 weeks prior to the first dose of study treatment.
 - Note: Individuals who have entered the follow-up phase of an investigational study may participate as long as it has been 4 weeks since the last dose of the previous investigational agent.
- 10. Diagnosis of any other malignancy within 3 years prior to enrollment, except for the following if adequately treated:
 - local basal cell or squamous cell carcinoma of the skin, or related localized non-melanoma skin cancer.
 - carcinoma in situ of the breast or of the cervix.
 - superficial bladder cancer.
 - Low grade (Gleason 6 or below) prostate cancer undergoing surveillance with no plans for treatment intervention or previously fully resected.

- 11. Gastrointestinal abnormalities including the following:
 - Inability to take oral medication.
 - Malabsorption syndrome or any other gastrointestinal condition (nausea, diarrhea, vomiting) that may impact the absorption of nanatinostat and valganciclovir.
 - Prior surgical procedures affecting absorption including total gastric resection.
 - Active gastrointestinal bleeding (hematemesis, hematochezia, or melena) in the past 3 months without documentation of resolution by endoscopy/colonoscopy.

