5.7. Prior and Concomitant Medications

Prior and concomitant medications include all vitamins, herbal remedies, over-the-counter, and prescription medications.

No other anticancer therapies (including chemotherapy, radiation, antibody therapy, immunotherapy, or other experimental therapies) of any kind are permitted while the patient is receiving treatment with nanatinostat, valganciclovir, and pembrolizumab. Patients are not allowed to participate concurrently in any other therapeutic study.

If a patient takes an exclusionary medication while on study, the event will be deemed a protocol deviation and continuation of that patient in the study will be decided by the Sponsor's Medical Monitor.

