5.7.4. Prohibited Therapies

Patients are prohibited from receiving the following therapies during the screening and treatment phases of this study:

- Anti-cancer systemic chemotherapy or biologic therapy.
- Immunotherapy not specified in this protocol.
- Chemotherapy not specified in this protocol.
- Investigational agents other than nanatinostat, valganciclovir and pembrolizumab.
- Radiation therapy.
- Tenofovir (unless the patient can be switched to an alternative ART).

- Live vaccines within 30 days prior to the first dose of investigational treatment and while participating in the study.
- Medications with a known risk of prolonging the QTc interval/TdP (Class Ia [disopyramide, quinidine, procainamide] and Class III [sotalol, dofetilide, ibutilide] antiarrhythmic agents) (Drew 2010). If, during the course of this study, the concomitant administration of drugs with a known potential to cause TdP is required and cannot be avoided, study drug administration must be interrupted until an assessment of the potential safety risk has been performed.
- Corticosteroids for any reason other than those outlined in Section 5.7.2.1.

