The initial informed consent form and any subsequent revised written informed consent form must receive approval and/or favorable opinion by the IRB/IEC in advance of use. The patient or his/her legally acceptable representative should be informed in a timely manner if new information becomes available that may be relevant to the patient's willingness to continue participation in the study. The communication of this information should be documented.

A copy of the signed ICF will be provided to the patient. The Investigator will retain all original versions of signed ICFs.

After informed consent is provided, patients who successfully complete all screening assessments and study entry criteria may be enrolled in the study. The period for completing screening assessments is 28 days.

An optional supplemental consent for future use of blood and tissue samples for research purposes (biobanking) may be proposed to patients based on local regulatory requirements. The assessments to be conducted on these samples are described as exploratory endpoints in the protocol.

Rescreening of patients is only allowed once per patient if the patient is not registered as entering the treatment phase (Cycle 1 Day 1). In this case, a new patient number will be assigned, and the patient will be identified with this number throughout their participation in the study.

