7.2.5. Baseline Disease Assessments

Any imaging assessments already completed during the regular work-up of the patient within 21 days prior to Cycle 1 Day 1, including before signing the main study ICF, can be considered as the baseline images if all imaging requirements for the study are met.

The imaging modality used for evaluation at screening must be consistently used throughout the study for each patient (CT with contrast or MRI). If positron emission tomography (PET) is used, a contrast-enhanced CT scan must be included.

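### Criterion 6 allows palliative radiotherapy that Sections 5.7 and 5.7.4 prohibit, and the baseline scan may predate locoregional radiotherapy to a target lesion

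*Protocol*

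**What the plan says.** Criterion 6 in Protocol Section 4.3 has two sentences. The first excludes patients who are "Less than 14 days from prior locoregional site radiotherapy"; the Synopsis carries the same rule. Neither place says from which event the 14 days are counted. The second sentence reads "Palliative radiotherapy outside the head and neck is allowed as long as the lesions are not target lesions". It sets no time limit, and the target-lesion restriction belongs to this sentence only.

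Section 5.7.4 opens with "Patients are prohibited from receiving the following therapies during the screening and treatment phases of this study", and its list contains the bare entry "Radiation therapy". That entry has no palliative exception and no pointer to criterion 6, although the entries for tenofovir, QT-prolonging drugs and corticosteroids each carry a qualification. Section 5.7 adds, for the time on study treatment: "No other anticancer therapies (including chemotherapy, radiation, antibody therapy, immunotherapy, or other experimental therapies) of any kind are permitted".

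On timing, Section 7.1 says "The period for completing screening assessments is 28 days". Section 7.2.5 accepts as baseline "Any imaging assessments already completed during the regular work-up of the patient within 21 days prior to Cycle 1 Day 1", including images taken before the study consent was signed, if they meet the imaging requirements. Section 6 sets the same 21-day window.

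Appendix 3 selects target lesions by size, organ representation and reproducibility. As printed, it has no rule for irradiated lesions. SAP Table 2 (Section 4.5.5.2) censors DOR and PFS at the last scan before a new anti-cancer treatment and does not mention radiotherapy. SAP Section 4.8 records that the study stopped before Phase 2 and that ORR became a primary efficacy endpoint for Phase 1b.

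**The concern.** There are two separate problems.

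The first is a contradiction. A site treating a painful lesion outside the head and neck during screening finds the treatment allowed in one section and prohibited in another. The answer decides whether it is a protocol deviation. If it happens on study, the answer may also decide whether PFS and DOR are censored.

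The second is a measurement gap. The target-lesion safeguard in criterion 6 stops outside the head and neck. Head-and-neck radiotherapy falls under the first sentence, which has only the 14-day limit. If the baseline scan was taken before that radiotherapy, any radiation shrinkage of a target lesion enters the change from baseline and is credited to study treatment. At stake is a response rate that is still to be reported, by dosing regimen, in very small cohorts.

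**Working it through.** The plan gives no figure on this point to reproduce. The check is day counting, the response table in Appendix 3, and an illustration of size.

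**Inputs**
- Locoregional radiotherapy limit: 14 days or more (criterion 6). Anchor assumed to be Cycle 1 Day 1.
- Baseline scan: Day -21 to Day -1 (Sections 6 and 7.2.5), possibly before consent.
- Screening: up to 28 days (Section 7.1).
- Cohorts of 3 to 6 patients (Section 3.1).
- Day -k means k days before first dose (SAP Section 4.1.5).

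**1. Where the rules collide.** Palliative radiotherapy to a non-target lesion outside the head and neck passes criterion 6 on every screening day and is prohibited by Section 5.7.4 on every screening day. If the second sentence of criterion 6 is also read as applying on study, the conflict extends through treatment. For locoregional radiotherapy the collision depends on the consent date. With consent on Day -28, treatment on Day -28 to Day -14 (28 - 14 + 1 = 15 days) passes criterion 6 but breaches Section 5.7.4. If it was finished before consent, there is no conflict.

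**2. Can the scan come first?** Earliest scan Day -21, latest permitted end of locoregional radiotherapy Day -14: 21 - 14 = 7 days. A sequence that breaks no printed rule is: routine scan on Day -21, radiotherapy to a neck lesion ending by Day -14, consent, dosing on Day 1 with that scan as baseline. If the scan is taken after consent, later radiotherapy falls in screening and Section 5.7.4 prohibits it. So, if the plan is followed, the route requires a pre-consent scan.

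**3. Can it produce a response?** PR needs at least a 30% fall in the target sum from baseline. An irradiated target lesion is part of that sum, so its shrinkage can contribute to or produce a PR. Irradiating only non-target lesions is different: in the Appendix 3 table, target SD with non-target non-PD stays SD. At most such radiotherapy turns a PR into a CR or masks non-target progression. It cannot turn SD into PR.

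**4. Size if one patient is affected.** One false response adds 1/6 = 16.7 points in a cohort of six and 1/3 = 33.3 points in a cohort of three. Clopper-Pearson 95% limits in a cohort of six move from 0% to 45.9% (0/6) to 0.4% to 64.1% (1/6). For the planned Phase 2 arm of 30, 7/30 gives a lower limit of 9.9% and 8/30 gives 12.3%. One patient could therefore have moved the lower limit across the 10% named in the sample-size text. That is a design-stage illustration only, since Phase 2 was not run. The documents give no frequency of recent radiotherapy, so an expected bias cannot be computed.

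**5. Effect of the contradiction on the analysis.** If on-study palliative radiotherapy counts as new anti-cancer treatment, Table 2 censors PFS and DOR at the last earlier scan. If it is allowed concomitant care, follow-up for progression continues. The SAP does not say which applies.

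**The case against.** The strongest reply is that criterion 6 is an entry criterion while Sections 5.7 and 5.7.4 govern conduct, so the two can coexist. This holds for locoregional radiotherapy finished before consent, and on treatment Sections 5.7 and 5.7.4 agree with each other. It does not hold for palliative radiotherapy during screening, a period that both texts govern.

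It is also fair that the measurement route is narrow. It needs a pre-consent scan in roughly the first week of the 21-day window, radiotherapy to a target lesion finished by Day -14, and prompt dosing. Sponsor review of eligibility (Section 7.2.6), recovery from acute toxicity (inclusion criterion 8) and exclusion criterion 23 on conditions that impair assessment reduce the route further. None of them closes it. Appendix 3 also defers to RECIST v1.1, whose full text is not in the documents, so a rule there on irradiated lesions cannot be ruled out.

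A reader might infer more than the documents support:
- That the palliative allowance itself produces false responses. It excludes target lesions, and the response table does not let non-target shrinkage turn SD into PR.
- That DOR is measured against a pre-radiation baseline. DOR runs from first response to progression or death, and target-lesion progression is judged against the smallest sum on study. Baseline affects only who enters the DOR set.
- That 7 of 21 window days means one third of patients are exposed. That is a share of calendar days, not a frequency.
- That every irradiated patient should count as a non-responder. This would penalise treatment of non-target lesions and could bias ORR downward.

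**Conclusion.** Both parts hold in limited form. The contradiction over palliative radiotherapy stands on the text and must be reconciled by the sponsor; this review does not say which rule is right. The measurement gap is real but narrow. Locoregional radiotherapy completed before consent can end up to about 7 days after the baseline scan, and shrinkage of a head-and-neck target lesion can then count toward a PR. This assumes that the 14 days run to Cycle 1 Day 1 and that no rule outside the printed appendix bars irradiated target lesions.

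The number of patients affected is not given and may be zero. The consequence is confined to the Phase 1b ORR, where a single false response is large relative to a cohort of 3 to 6, and to membership of the DOR set. How Table 2 treats on-study palliative radiotherapy remains open for PFS and DOR.

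**What to change.** - **Protocol wording.** Reconcile criterion 6 (Section 4.3 and Synopsis) with Sections 5.7 and 5.7.4, and state the event from which the 14 days are counted.
- **Measurement rule.** Require either that a lesion irradiated after the baseline scan is not used as a target lesion, or that the baseline scan follows the radiotherapy. Enrolment has stopped, so this matters for the design and any successor study rather than for patients already treated.
- **SAP flag.** Identify patients with a target lesion irradiated between the baseline scan and first dose, or on study.
- **SAP sensitivity analysis.** Repeat the Phase 1b ORR with flagged patients' responses counted as non-response and kept in the denominator. Do not flag patients irradiated only at non-target lesions.
- **SAP Table 2.** State whether on-study palliative radiotherapy counts as new anti-cancer treatment.

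The cost is small: one extra analysis and, under the measurement rule, an occasional repeat baseline scan. Prior radiotherapy dates are collected (Protocol Section 7.2.3). That section does not say that the irradiated site is recorded, so a few source queries may be needed. If no patient is flagged, one sentence in the study report closes the ORR question.
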